13.4.5 Adverse Events

AEs will be coded using the latest available version of the MedDRA, the version of which will be provided in the clinical trial report.

Pre-treatment AEs are AEs with onset prior to the intake of the contrast agent (Visit 1) that either stop prior to first administration of trial drug or are ongoing but do not deteriorate with respect to severity and/or relationship to trial drug after start of trial treatment. Pre-treatment AEs will be listed separately and will not be included in the AE tabulations. All other AEs will be considered as treatment-emergent AEs (TEAEs) and will be summarised per treatment group for the whole trial period.

An overall summary table will be provided showing the number and percentage of subjects with any:

- AE
- TEAE
- Severe TEAE

- Serious TEAE
- AEs leading to withdrawal
- Drug-related TEAE
- Drug-related severe TEAE
- Drug-related serious TEAE
- TEAE leading to withdrawal
- TEAE with outcome death

The two-sided p-values of Fisher's exact test for the 3 comparisons "Lumentin® 44 versus diluted Omnipaque®", "Lumentin® 44 versus p Movprep®" and "diluted Omnipaque® versus Movprep®" with regard to the percentages of subjects affected will be given in the overall summary table. The number of reported AEs will also be shown in this summary table.

The above summary table may be repeated, stratified by randomisation stratification factors.

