7.2.3 Safety Variables

The safety parameters consist of:

- Especially solicited adverse events (AEs), i.e. stomach ache, burping, letting go of wind, Nausea and sensation of fullness
- Any treatment emerging adverse events
- Any treatment emerging adverse drug reactions (ADR)
- Safety laboratory evaluations (clinical chemistry)
- The reasons for withdrawal from the trial

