10.3 Reporting of Adverse Events

All trial subjects will be carefully monitored for the occurrence of AEs during the trial period, from start of intake of the first dose until the contact 2, telephone interview 12 – 48 hours after the CT-examination. Reported AEs will be followed up (see 10.4 below). The Investigator will collect AEs with a non-leading question such as “have you experienced any new health problems or worsening of existing conditions” as well as reporting events directly observed or spontaneously volunteered by subjects.

Clearly related signs, symptoms and abnormal diagnostic procedure results should be grouped together and reported as a single diagnosis or syndrome whenever possible.

All AEs including but not limited to events reported by the subject, or reported in answer to an open question by the Investigator or member of this team, which fall into any of the above definitions must be recorded as an AE in the eCRF and should include the following information:

- Brief description of the event (diagnosis)
- Start date (and time, if relevant)
- Stop date (and time, if relevant) (or resolution)
- Severity
- Action taken regarding trial treatment
- Opinion on causality

- Seriousness
- Outcome

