- Magknip¶
- Mättnad¶
- Rapningar¶
- Vädersläpp¶
- Illamående¶

¶

Har patienten rapporterat någon av ovan biverkningar? ☐

Jaa	Nej
☐	☐

¶

¶

Om patienten svarar ja på denna fråga så fylls patientjournalens "AE form" i. Använd en AE form för varje enskild biverkan. ¶

¶

¶

OBS!¶

Alla biverkningar som anses vara allvarliga eller utifrån prövarens åsikt behöver följas upp skall följas upp i enlighet med protokollet. Om någon av de biverkningarna som rapporterats vid uppföljningssamtalen faller inom någon av dessa kategorier skall patienten informeras om att han/hon kommer att bli kontaktad igen av prövaren. ¶

¶

¶

¶

¶

¶

Datum: ☐

☐	☐	☐	☐	☐	☐	☐
Å	Å	M	M	D	D	

☐

☐

☐	☐	☐	☐	☐
T	T	M	M	

☐

☐

Intervjuares signatur: ☐

☐	☐	☐	☐	☐	☐	☐	☐	☐	☐	☐	☐
☐	☐	☐	☐	☐	☐	☐	☐	☐	☐	☐	☐

☐

¶

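### The only between-arm adverse event tests are on pooled any-event rows, so a difference confined to one solicited symptom is diluted, and the recording rules may not preserve the symptom-level data

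*Combined protocol and SAP*

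**What the plan says.** Safety and tolerability of each of the three agents is a stated secondary objective (6.2). The first safety variable in 7.2.3 is "Especially solicited adverse events (AEs), i.e. stomach ache, burping, letting go of wind, Nausea and sensation of fullness".

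Appendix 3, the form for the telephone contact at 12 to 48 hours, lists the five symptoms and gives a single yes/no box for all of them: "Har patienten rapporterat någon av ovan biverkningar" (has the patient reported any of the above side effects). If yes, the instruction is "Använd en AE form för varje enskild biverkan" (use one AE form for each individual side effect). A checklist symptom thus becomes an adverse event.

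Section 13.4.5 then plans: "An overall summary table will be provided showing the number and percentage of subjects with any" of ten categories: AE, TEAE, severe TEAE, serious TEAE, AE leading to withdrawal, three drug-related categories, TEAE leading to withdrawal, and TEAE with outcome death. The test is attached to this table: "The two-sided p-values of Fisher's exact test for the 3 comparisons", that is, all three pairs of arms. The number of reported AEs is shown as well. Of the rest it says "AEs will be coded using the latest available version of the MedDRA" and that TEAEs "will be summarised per treatment group for the whole trial period", without naming a level such as system organ class, preferred term or solicited symptom.

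On recording, 10.3 says: "Clearly related signs, symptoms and abnormal diagnostic procedure results should be grouped together and reported as a single diagnosis or syndrome whenever possible".

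**The concern.** A named safety variable has no analysis of its own. Its five components are merged with each other and with all unsolicited events before any test is made. If one of them, say nausea, is more frequent on Lumentin, the any-TEAE row shows that only through subjects who had no other event. The more common the other symptoms are, the fewer such subjects remain.

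The risk is one of interpretation: a non-significant any-TEAE row could be reported as similar tolerability when the arms differ on a symptom that matters for a drink of about one litre.

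There is also a data problem that needs no assumed rates. Section 10.3 pulls towards one grouped diagnosis, and Appendix 3 towards one form per event. The same subject could yield one AE or several depending on who completes the form, and a grouped term may not be separable into symptoms later.

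**Working it through.** **The plan's own figure.** The only power stated is for the primary variable (13.6.1): difference 1.50, SD 2.00, 40 v 20, two-sided 5%. The standardised difference is 1.50 / (2.00 × √(1/40 + 1/20)) = 2.739, and Φ(2.739 − 1.960) = 0.782, which agrees with the stated 78%. No power is stated for safety.

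**Inputs for the safety check.**
- Arm sizes 40 v 20, from 8.4 and 13.6.1. (Section 8.5 says 1:1:1, which needs reconciling separately.)
- Fisher's exact test, two-sided 5%, unadjusted, from 13.2 and 13.4.5.
- Symptom rates: all assumed, because the documents give none.

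**Formulas.** Let p be the rate of the symptom of interest and b the proportion of subjects with at least one other checklist symptom, equal in both arms and independent of the first.
- Any-event rate = 1 − (1 − b)(1 − p).
- Exact power = the sum, over all outcomes (x of 40, y of 20) with Fisher p < 0.05, of Bin(x; 40, rate on Lumentin) × Bin(y; 20, rate on comparator).

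**Result for p = 40% on Lumentin v 5% on a comparator.** Tested alone, power is 88%. In the pooled row:

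| b | Any event, Lumentin | Any event, comparator | Power |
|---|---|---|---|
| 10% | 1 − 0.9 × 0.60 = 46% | 1 − 0.9 × 0.95 = 14.5% | 66% |
| 20% | 52% | 24% | 48% |
| 40% | 64% | 43% | 27% |
| 60% | 76% | 62% | 17% |
| 80% | 88% | 81% | 10% |

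**Different inputs.** Take one symptom at 50% v 10% and the other four each at rate q in both arms. Tested alone, power is 89%. The pooled row has the following power, with independent symptoms and, in brackets, with correlation 0.5 (Gaussian copula):
- q = 2%: 77% (80%)
- q = 5%: 59% (64%)
- q = 10%: 43% (40%)
- q = 20%: 23% (18%)
- q = 30%: 14% (11%)

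At low background the loss is modest. From about q = 10% it is large, and correlation does not remove it.

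**The opposite case.** If three independent symptoms each rise from 5% to 25%, the any-event rates are 1 − 0.95³ = 14% and 1 − 0.75³ = 58%. The pooled row then has 91% power, against 46% for one symptom alone. If all five rise from 10% to 30%, the figures are 90% and 37%.

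**Multiplicity if each symptom is tested.** Five symptoms × three pairs = 15 tests. If these were independent at 5%, the chance of at least one false positive would be 1 − 0.95¹⁵ = 54%.

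**The case against.** The strongest reply is that the size depends on rates nobody has stated. Section 5.3 says only that eructation, abdominal distension and mild nausea were the commonest effects in pilot volunteers given the 60%-air foam; it gives no percentages and nothing on the comparators. The checklist is used only at the telephone call, while 10.3 describes a non-leading question. This stands: the loss is a range, not a figure.

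Nor does pooling always hurt. For a foam, several gastrointestinal symptoms rising together is plausible, and the pooled row is then the better test. This also stands, and is why the pooled rows should stay.

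The plan has other content too. Mild symptoms do not fill the severe, serious, withdrawal or death rows. Fullness has its own comparison as a secondary efficacy variable (7.2.2, 13.4.2). Events are MedDRA-coded, 13.2 promises frequency tables for categorical data, and section 13 allows a separate SAP. These points narrow the concern but do not remove it. Nausea, stomach ache, burping and wind have no comparison of their own, the level of the TEAE summary is open, and the SAP is optional.

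Finally, 10.3 and Appendix 3 might coexist if one form is used per grouped diagnosis. Grouping does not change whether a subject has any TEAE, so it does not affect the pooled Fisher rows. It does affect the number of AEs shown in the same table, and whether a symptom breakdown can be recovered.

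**Conclusion.** The pooled table is the only specified between-arm AE comparison, and a difference confined to one solicited symptom loses power in it. For 40% v 5%, power falls from 88% to between 66% and 10% as the proportion of subjects with another checklist symptom goes from 10% to 80%. This rests on assumed rates, independence, equal background in the arms and 40 v 20 subjects. It concerns the any-AE and any-TEAE rows and probably the drug-related TEAE row. The tension between 10.3 and Appendix 3 rests on the text alone.

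A reader might infer that the any-event rows will saturate, so that a symptom difference is hidden and cannot be shown. The documents do not support that. Saturation needs high background rates that they never give: even with all 40 Lumentin subjects affected, Fisher's test still reaches p = 0.033 against 17 of 20, and fails (p = 0.107) only from 18 of 20. A descriptive TEAE summary could also reveal the symptom. Dilution, of unknown degree, is what can be said.

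**What to change.** In 13.4.5, keep the pooled rows and make two additions:
- A by-arm table of each solicited symptom: number and percentage of subjects, severity, and the difference with 95% confidence interval for Lumentin against each comparator.
- TEAEs split into solicited and unsolicited.

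If p-values are shown for these rows, label them descriptive or adjust them for multiplicity. Section 13.2 as written would call any of them below 5% statistically significant.

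Reconcile 10.3 with Appendix 3 before enrolment, so that each solicited symptom is always recorded under its own term. The analysis table can be added later, but a symptom absorbed into a grouped diagnosis may not be recoverable.

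The cost is protocol wording and a few more table rows, from AE forms already planned. The downside is more nominal comparisons if p-values are included; differences with intervals alone would avoid reporting them.

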13.5 Interim Analyses

An interim analysis is not planned.

13.6 Determination of Sample Size

13.6.1 Sample size (per group)

The standard deviation of the primary variable (i.e. the difference in contrast density in HU between bowel lumen and wall (mucosal lining), expressed as the mean of 9 measurements performed in the 5 selected sub-segments of the small bowel) is estimated from the first pilot clinical study of abdominal CT examinations on healthy volunteers using a slightly different formulation (L60). Based on data from that study [1] it is assumed that the standard deviation will be around 2.00 and the difference between Lumentin® 44 and Omnipaque® as well as the difference between Lumentin® 44 Movprep will be 1.50. Then 40 fully evaluable patients in the Lumentin group and 20 patients in each of the comparator groups are needed to get 78 % power for each of the two primary objectives (no adjustment for multiplicity). This means that the total probability in the trial to get a p-value less than 5 % in the test of both the primary objectives is $0.78 \times 0.78 = 0.61$.

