Statistical analyses	
The sample size estimation is based on a similar variable as the primary variable in this trial, i.e. the difference in contrast density in HU between bowel lumen and wall (mucosal lining), expressed as the mean of 9 measurement performed in the 5 selected sub-segments of the small bowel. At each measurement site, the equipment gives a mean value (given by the software of the X-ray equipment in Hounsfield Units) and a standard deviation (for the pixels in the Region of Interest, ROI). This mean value is from now on called “mean contrast density”.
 
In order to reach a 78 % probability (power) to detect (i.e. get a two-sided p-value less than 5 %) assuming a difference of 1.50 between the groups for the mean difference in contrast density and a standard deviation of 2.00 (assumptions based on an earlier trial, [1]) a total of 40 fully evaluable is needed in the Lumentin group and 20 in each of the comparator groups, i.e. a total of 80 fully evaluable subjects
 
The randomisation will be stratified by gender as the drinking capacity on average differs between males and females.
 
Descriptive statistics will be used to describe the results. When testing the hypotheses of equality between the groups p-values (two-sided) will be calculated by means of the Wilcoxon rank sum test or Fisher's exact test depending on the distribution of the variable of interest.

-----------------------------	---

1.1 Schedule of Events:

Visit/Contact	0 Screening ^{a)}	1 CT-scan	2 Telephone interview and early termination ^{b)}
Day	-28 to -1	0	1-2
Visit window			12-48 hours
Subject information	X	X	
In/exclusion criteria		X	
Informed consent		X	
Pregnancy test ^{c)}		X	
Randomisation		X	
Subject demographics (incl. height and weight)		X	
Concomitant treatment		X	X
Concomitant illnesses		X	
Medical history		X	
Blood sample (clinical chemistry) ^{d)}		X	
Adverse event(s)		X	X
Dispensing of contrast agent		X	
Administration of Iodine contrast		X	
CT Scan		X	
Evaluation of contrast difference		X	
Evaluation of extension and distension composite score		X	
Evaluation of diagnostic ability		X	
Evaluation of contrast agent degradation		X	
Subject assessment of taste, smell, consistency etc.		X	
Compliance		X	

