5 BACKGROUND

5.1 Introduction

Subjects referred for examination with computed tomography, CT, of the abdomen are, according to clinical practice, prepared with an oral liquid contrast for demarcating loops of small bowel from surrounding tissues and abdominal and pelvic organ. Most often these oral contrast-agents are based on iodine, so-called positive contrast agent, which results in a bright bowel content, i.e. an intraluminal appearance with positive Hounsfield units, HU. Other options include iso-osmotic solutions based on either polyethylene glycol or Sorbitol / Mannitol, creating luminal densities near that of water, i.e. around 10-20 HU, hence by rights denominated as neutral oral contrast agents. The rationale behind administering a neutral solution is to establish a boosted attenuation difference between the small bowel wall and its lumen, further increased by an intravenously administered iodine contrast. The amplified difference between small bowel wall and lumen might theoretically result in augmented conspicuity of the interface itself, thereby improving diagnostics of the mucosal lining and of lesions in the bowel wall and its proximity. This knowledge is implemented in CT protocols aiming at pancreatic cancer, where neutral contrast is recommended, especially in the papillary part of duodenum, in order to increase the probability of detection of small tumours. A high attenuation difference between small bowel lumen and mucosal lining is also a prerequisite for virtual 3D-presentation of the small bowel, similar to CT-colonoscopy.

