5.2 Rationale

Lument AB have been successful in developing a food-based oral product, characterized by being a true negative CT-contrast agent by providing a density contrast down to minus 600 HU. Necessary demands included in the research work were palatability (taste, smell and consistency), stability during its passage through the upper gastro-intestinal tract, and acceptable side effect profile. After approval from the local Ethical Committee (Dnr. 2015/912) and Institute of Radiation Protection (Dnr. SSF02015-048) we successfully accomplished our first pilot clinical study [1] of abdominal CT examinations on healthy volunteers using a slightly different formulation containing 60% air as compared to the current formulation containing 44% air. The results showed that the foam provided true negative, black bowel lumen, from pylorus to cecum; good acceptance of the foam by the volunteers with only mild adverse events reported, and that the diagnostic reading of the CT-examination as a whole, with “black” loops of small bowel, was easily accepted by the radiologist.

Lumentin® 44

Lumentin® 44 is a novel, HU-negative contrast agent which is formulated as an aqueous dispersion containing less than 4% dry matter. The product consists of a continuous aqueous phase that contains egg white protein (EWP) as foaming agent, xanthan gum as stabilizer, phosphate salts as buffering agents, and flavouring.

Prior to use, the product is whipped to a stable foam, containing 44% air, which is orally administered. The whipped, ready to use, Lumentin® 44 foam formulation is stable with suitable characteristics (air content, volume, bubble size, homogeneity, consistency, stability and palatability). A typical dose for an Abd-CT examination is 1000 ml ± 200 ml taken orally over a period of 45 to 60 minutes.

The air trapped in the foam is the radiological key ingredient that causes improved bowel lumen-to-wall contrast, with the interface at the surface of the mucosal lining of the bowel wall. The external demarcation of the small bowel from surrounding organs is on par with standard filling agents used in Abd-CT examinations of today.

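### The 1.50 difference used for sample size, stated for a variable in HU, contradicts the protocol's own density figures, so the 78% and 61% power are not tied to the primary variable

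*Combined protocol and SAP*

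**What the plan says.** Section 13.6.1 identifies the variable and its unit: "The standard deviation of the primary variable (i.e. the difference in contrast density in HU" between bowel lumen and wall, averaged over nine sites. From the pilot study of the 60% air foam in healthy volunteers, "it is assumed that the standard deviation will be around 2.00 and the difference between Lumentin® 44 and Omnipaque", and equally the difference from Movprep, will be 1.50. With 40 evaluable subjects on Lumentin and 20 on each comparator it states 78% power per comparison. It gives "the total probability in the trial to get a p-value less than 5 % in the test of both the primary objectives" as 0.78 × 0.78 = 0.61.

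The synopsis (Statistical analyses) says that a variable similar to the primary one was used, then describes it as "i.e. the difference in contrast density in HU between bowel lumen and wall (mucosal lining), expressed as the mean of 9 measurement". It states the 78% as "assuming a difference of 1.50 between the groups for the mean difference in contrast density and a standard deviation of 2.00".

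On density levels:
- Section 5.2: "Lumentin® 44 is a novel, HU-negative contrast agent".
- Section 5.1, on polyethylene glycol and sorbitol/mannitol solutions: "creating luminal densities near that of water, i.e. around 10-20 HU". Table 3 in section 9.1.3 lists macrogol as the main ingredient of Movprep.
- Section 5.1, on iodine agents: "which results in a bright bowel content, i.e. an intraluminal appearance with positive Hounsfield units". No figure is given.
- Section 10.1.1 sets the wall to +80 HU for every measurement and says that both comparators have a contrast like that of the wall.

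Section 13.4.1 plans a Wilcoxon rank sum test for each comparison and requires both to be significant.

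**The concern.** A group difference of 1.50 HU would make a negative-contrast foam and a neutral or positive liquid almost the same density. That is the opposite of the product's rationale. If 1.50 and 2.00 belong to some other scale, the power statement describes a variable that the trial does not analyse as primary.

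The 78% and 61% are the only quantitative justification for 80 evaluable subjects. As written, a reader cannot tell what difference in HU the trial is able to detect, or how likely it is to meet its own success rule.

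**Working it through.** **Reproducing the stated power.** Inputs from 13.6.1: difference 1.50, SD 2.00, 40 against 20, two-sided 5%.
- Standardised difference: 1.50 / 2.00 = 0.75.
- Standard error factor: √(1/40 + 1/20) = 0.2739.
- Noncentrality: 0.75 / 0.2739 = 2.739.
- Normal-approximation power: Φ(2.739 − 1.960) = 0.782. The noncentral t with 58 df gives 0.768.
- Joint figure as stated: 0.78 × 0.78 = 0.608.

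The equal-group formula in 13.6.2 causes no numerical error. It asks for 26.5 per group at 78%, and 40 against 20 is equivalent to 2 / (1/40 + 1/20) = 26.67 per group.

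**Checking 1.50 against the density levels.** The same +80 HU is subtracted in every arm, so the group difference is lumen HU minus lumen HU. An HU-negative foam lies below 0 HU.

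| Comparison | Source for comparator lumen | Comparator lumen | Implied difference (absolute) |
|---|---|---|---|
| Movprep | 5.1 with Table 3 | about 10-20 HU | at least about 10 HU |
| Movprep | 10.1.1 | about 80 HU | at least about 80 HU |
| Omnipaque | 5.1 | positive, no figure | above 0 only |
| Omnipaque | 10.1.1 | about 80 HU | at least about 80 HU |

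Sections 5.1 and 10.1.1 disagree about Movprep, but 1.50 fails on either.

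Reading backwards, a 1.50 HU difference would put the foam lumen at 10 − 1.5 = 8.5 to 20 − 1.5 = 18.5 HU (5.1), or at 80 − 1.5 = 78.5 HU (10.1.1). Both are positive, against 5.2.

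**What the mismatch does to the power figure.** Keeping SD 2.00 HU, a 10 HU difference has noncentrality 10 / (2 × 0.2739) = 18.26 and power above 99.9%. For 78% to hold, the SD would have to be 10 / 0.75 = 13.3 HU, or 80 / 0.75 = 106.7 HU at an 80 HU difference. These SDs are back-solved to show the inconsistency. They are not estimates.

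**Joint power.** The two statistics share the 40 Lumentin subjects. Their correlation is (1/40) / (1/40 + 1/20) = 1/3. The bivariate normal joint power is then 0.643, not 0.608.

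**Planned test.** Simulated Wilcoxon power at 0.75, with normal data, equal SDs and 40:20:20 (200,000 runs, continuity correction), is 0.742 per comparison and 0.587 jointly. With the shift held at 0.75 comparator SDs, power per comparison is about 88% if the Lumentin SD is half the comparator's and about 37% if it is double.

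**The case against.** The arithmetic is right, and the inputs come from a pilot report that is cited as a manuscript and cannot be seen here. The synopsis does say that a similar variable was used, so 1.50 and 2.00 may sit on a relative or transformed scale. This has some force: the documents cannot settle where the numbers came from. It does not rescue the text, because 13.6.1 calls the variable the primary one, in HU, and neither place gives another unit or a conversion. Nor is 1.50 offered as a minimum difference worth detecting. Section 13.6.1 assumes that the difference will be 1.50.

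Three limits on the point stand:
- Only the difference is contradicted. No second SD in HU is given, so 2.00 is unverifiable rather than shown to be wrong.
- The 10 HU floor applies to Movprep, and joins a statement about a class of agents to an ingredient list. For Omnipaque, 5.1 gives only a sign, and the 80 HU figure rests on a qualitative remark in 10.1.1.
- The two secondary faults partly offset each other. Allowing for the shared arm raises joint power (0.61 to 0.64), while using the Wilcoxon test lowers it (to about 0.59). The net change is about 2 points under normal data and equal SDs.

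A reader might infer that the trial is underpowered, or that N should change. The documents do not support that: the density levels point to a difference far larger than 1.50 HU. A reader might equally infer that true power exceeds 99.9%. That is not supported either, because it keeps the unverified SD of 2.00.

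**Conclusion.** This is an internal inconsistency, and the text is wrong as written. The assumed 1.50 HU is smaller than the protocol's own levels allow: at least about 10 HU for Movprep, or about 80 HU or more for both comparators on the reading in 10.1.1. The 78% is correct for a standardised difference of 0.75, but nothing ties 0.75 to the variable in 10.1.1. Power for the named primary variable is therefore undocumented, in either direction.

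Separately, 0.61 rests on an independence that the shared Lumentin arm rules out, and 78% is a normal-approximation figure for a trial that will use the Wilcoxon test. At 0.75 the planned test has about 74% power per comparison and 59% jointly. Those two figures assume normal data and equal SDs and are sensitive to the second assumption, so they illustrate the gap and should not be adopted as they stand.

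**What to change.** Keep N. In 13.6.1 and the synopsis, do one of the following:
1. Restate the difference, SD and power in HU for the 10.1.1 variable from the pilot data, and say how results with the 60% air foam carry over to 44% air.
2. State the scale on which 1.50 and 2.00 were obtained, and remove the attribution to HU.

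Under either option, name in the synopsis the variable actually used. Replace 78% and 0.78 × 0.78 = 0.61 with per-comparison and joint power for the Wilcoxon test, allow for the shared Lumentin arm, and state the assumed distribution and the SD in each arm.

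The cost is rewording and one recalculation from data that 13.6.1 already cites. Endpoint, test, significance level and success rule do not change. The quoted power may become slightly less favourable: at 0.75 with normal data and equal SDs it falls by about 4 points per comparison and 2 points jointly.

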13.4.1 Primary Efficacy Analysis

There are two primary objectives

- to compare the primary efficacy variable between patients randomised to Lumentin® 44 and patients randomised to diluted Omnipaque®
- to compare the primary efficacy variable between patients randomised to Lumentin® 44 and patients randomised to Movprep

The null-hypothesis that the primary efficacy variable is equal in the groups will be tested by means of the Wilcoxon rank sum test. In each of these analyses a two-sided p-value less than 5 % is considered statistically significant. A successful result is that both these tests are statistically significant and hence there is no need for multiplicity adjustment. The randomisation is stratified by gender but the statistical analysis of the primary objective will not be stratified.

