13.6.2 Sample Size Formula

The following formula has been used to calculate the number of patients needed [13] per group ($N_{\text{per group}}$):

$$N_{\text{per group}} = \frac{2 \times \sigma^2 \times (\lambda_\alpha + \lambda_\beta)^2}{\Delta^2}$$

In the formula above σ is the standard deviation, Δ is the difference to detect between the groups, λ_α is the $1-\alpha$ percentile of the standardized normal distribution and λ_β is the $1-\beta$ percentile of the standardized normal distribution. If the test is two-sided and the

significance level should be 0.0500 then $\lambda_\alpha = 1.9600$. If the power is 80% then $\lambda_\beta = 0.8416$ and if the power is 90% then $\lambda_\beta = 1.2816$.

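### The stated 78% power per comparison belongs to a z-test, not to the planned Wilcoxon test (about 74% to 75% with normal data), and the joint 61% treats two tests that share the Lumentin arm as independent

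*Combined protocol and SAP*

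**What the plan says.** The primary analysis (13.4.1) consists of two comparisons, Lumentin 44 against diluted Omnipaque and Lumentin 44 against Movprep. On the method it says: "The null-hypothesis that the primary efficacy variable is equal in the groups will be tested by means of the Wilcoxon rank sum test". On the level: "In each of these analyses a two-sided p-value less than 5 % is considered statistically significant". On success: "A successful result is that both these tests are statistically significant and hence there is no need for multiplicity adjustment".

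The sample size section (13.6.1) assumes an SD of 2.00 and a difference of 1.50 for each comparison. It says that 40 evaluable Lumentin subjects and 20 in each comparator group are "needed to get 78 % power for each of the two primary objectives (no adjustment for multiplicity"). It then gives "the total probability in the trial to get a p-value less than 5 % in the test of both the primary objectives" as 0.78 × 0.78 = 0.61.

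Section 13.6.2 introduces a normal-theory formula for two means in equal groups with the words "The following formula has been used to calculate the number of patients needed [13] per group". It contains no adjustment for a rank test.

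The synopsis (Statistical analyses) carries the single-comparison figure only: "In order to reach a 78 % probability (power) to detect".

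**The concern.** A power figure should belong to the test that will be run and to the rule by which the trial is judged. Here the formula is for means and the test is on ranks, so the power of each comparison may be misstated. Success needs both tests, and both draw on the same Lumentin subjects. Multiplying the two powers is therefore not valid, and the synopsis gives no figure for the success rule at all. At stake is whether the sponsor and the ethics committee are given the right chance of a successful trial, and whether anyone can reproduce it from the text.

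**Working it through.** **Inputs.** Difference 1.50 and SD 2.00 for each comparison, and 40:20:20 evaluable subjects (13.6.1). Two-sided 5% per test, Wilcoxon rank sum, both tests required (13.4.1). The plan names no distribution. Normal data with equal SDs are assumed below because the formula in 13.6.2 has a single σ and uses normal percentiles. Power is stated for evaluable subjects, so dropout does not enter.

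**Step 1: reproduce the 78%.** With known SD:

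- standard error = 2.00 × √(1/40 + 1/20) = 0.548
- standardised difference = 1.50 / 0.548 = 2.739
- power = Φ(2.739 − 1.960) = Φ(0.779) = 78.2%

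This matches the plan. The product 0.78 × 0.78 = 0.608 also matches the stated 0.61.

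**Step 2: allow for an estimated SD.** The noncentral t with 58 degrees of freedom gives 76.8%.

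**Step 3: use the planned test.** 400,000 trials were simulated with normal data, SD 2.00, a shift of 1.50, and one Lumentin arm of 40 compared with two arms of 20. The exact two-sided test rejects when the smaller U statistic is at most 274 (actual size 0.0485).

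- Exact or continuity-corrected Wilcoxon: 74.2% per comparison
- Normal approximation without continuity correction: 74.8%

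A large-sample shortcut, the z-test with asymptotic relative efficiency 3/π, gives 76.3%. Noether's approximation gives 72.4%. The direct calculation lies between them.

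**Step 4: joint power.** The two statistics share the Lumentin mean, so on the z-scale their correlation is (1/40) / (1/40 + 1/20) = 1/3.

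| Test | Per comparison | Both, if multiplied | Both, arm shared |
|---|---|---|---|
| z-test (as in the plan) | 78.2% | 61% | 64.3% |
| t-test | 76.8% | 59% | 62.7% |
| Wilcoxon, exact | 74.2% | 55.1% | 58.8% |
| Wilcoxon, uncorrected | 74.8% | 55.9% | 59.5% |

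The stated 61% is too low for z-tests by about 3 points and too high for the Wilcoxon tests by about 2.

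**Step 5: dependence on the distribution.** Keeping the same difference and SD, simulated Wilcoxon power per comparison at 40 v 20 is about 71% for uniform data (70% with the exact test), 74% to 75% for normal, 79% for logistic, 83% for t with 5 degrees of freedom and 86% for Laplace.

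**Step 6: the printed formula.** With 1.960 and 0.772 (78% power), 2 × 2.00² × (1.960 + 0.772)² / 1.50² = 26.5 per group. The equal-group equivalent of 40 v 20 is 2 / (1/40 + 1/20) = 26.7. The formula and the 40:20 split therefore agree on 78%. The conversion to unequal groups is simply not shown.

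**The case against.** The strongest reply is that nothing here is miscalculated: 78% reproduces, and so does the product. That is right. A reader might infer an arithmetic slip, and the documents do not support that. The fault is that the figure belongs to another test.

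Second, 74% is not a property of the plan's inputs alone. No distribution is given, and with logistic or heavier tails the Wilcoxon test reaches or passes 78%. This stands: the lower figure must be quoted with its assumption. It does not rescue the text, because the plan makes no heavy-tail argument and its formula is the normal-theory one.

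Third, the joint figure is nearly right: about 59% against 61%, and 13.6.1 states it openly next to the 78%. This also stands. A reader might infer that the chance of success is badly overstated or concealed. It is neither; the synopsis abbreviates. But the agreement is accidental. Correcting only the test would give about 55%, and correcting only the correlation would give 64.3%.

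Fourth, two sharper charges against 13.6.2 are tempting and fail. One is that the equal-group formula cannot yield 40 and 20; step 6 shows that it is consistent with them. The other is that calling λ_α the 1−α percentile spoiled the calculation. Read literally for α = 0.05 (1.645), the label would give 20.8 per group, but the same section gives 1.9600 for a two-sided test, which is the value behind the 78%. The label is a clerical looseness.

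Finally, one may doubt whether a difference of 1.50 and an SD of 2.00 suit an endpoint in Hounsfield units. That is a separate question. This check takes both values as given, so it says nothing about power under other inputs.

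**Conclusion.** The point holds as a mismatch between the stated power and the planned tests. Under normal data with equal SDs, a difference of 1.50, SD 2.00 and 40 v 20 evaluable subjects, each Wilcoxon comparison has about 74% to 75% power, 3 to 4 points below the stated 78%. For the success rule the power is about 59%, against the stated 61%. The independence assumption behind the 61% is invalid, but its error runs in the opposite direction to the error from the choice of test, so the joint fault is one of method more than of size. The per-comparison shortfall is conditional on the distribution and vanishes for logistic or heavier-tailed data. The test, significance level, numbers and success rule are not called into question by this point.

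**What to change.** - **13.6.1:** state about 74% per comparison and about 59% for both tests. Say that these come from simulating the Wilcoxon tests at 40:20:20 with the Lumentin arm shared, and name the normal, equal-SD assumption. Remove the multiplication.
- **Synopsis, Statistical analyses:** add the both-tests figure beside the single-comparison one, because success requires both.
- **13.6.2, tidying only:** show the unequal-allocation form, with 2/N replaced by 1/n1 + 1/n2, so that the link to 40 v 20 is visible. Label 1.96 as the 1−α/2 percentile.

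The cost is wording and one short simulation. No patients are added. The only downside is that the stated power becomes slightly less favourable.
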